This study sought to evaluate a mobile self-management program integrating Positive Psychology (PP) and Behavioral Activation (BA) as a mental health intervention for young adults in South Korea. The program was grounded in established theoretical frameworks and designed to (1) enhance positive emotional experiences, (2) help participants identify their personal strengths, (3) encourage engagement in strengths-based activities, and (4) support planning for a meaningful and fulfilling future. These goals drew on PP principles while incorporating BA techniques to promote and sustain positive affect and adaptive behaviors in young adults. Using a randomized controlled trial design, the study examined the program's effectiveness in improving psychological outcomes—including stress, depression, anxiety, and resilience—among young adults with elevated stress, as well as its usability and perceived quality.

Primary Objective:

- To evaluate whether a mobile self-management program integrating PP and BA reduces perceived stress in young adults with elevated stress.
- To assess whether the program improves depression, anxiety, and resilience.

Secondary Objectives:

- To evaluate usability and perceived quality of the mobile interventions.

3. Study Design

This study employed a randomized controlled trial with a wait-list control design to evaluate the effects of a mobile-based self-management program for young adults experiencing elevated stress in community settings in South Korea.

4. Study Setting

Participants were recruited nationwide in South Korea through both offline and online platforms. Recruitment sites included youth centers, mental health welfare centers, and a suicide prevention center. The intervention was delivered entirely via a mobile application, and outcome assessments were conducted online.

5. Eligibility Criteria

Inclusion Criteria:

- Age 19–34 years at the time of participation
- Proficiency in using digital devices
- Use of an Android-based smartphone or tablet
- Score ≥ 14 on the Perceived Stress Scale–10 (PSS-10)
- Provision of informed consent for random assignment

Exclusion Criteria:

- Score < 14 on the PSS-10
- Declines random assignment

6. Interventions

Experimental: Intervention Group

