Participants assigned to the intervention group received a text message with a link to install the *DodaMe* mobile self-management program, which integrates Positive Psychology (PP) and Behavioral Activation (BA). The intervention lasted eight weeks, consisting of:

- **Guided Phase (Weeks 1–4):** Weekly objectives included (1) enhancing positive affect, (2) identifying personal strengths, (3) applying strengths in daily life, and (4) planning for a positive future. Program activities involved emotional check-ins, gratitude journaling, mindfulness practice, positive behavioral tasks, and goal setting.
- **Self-Directed Phase (Weeks 5–8):** Participants voluntarily selected from 10 recommended activities tailored to their strengths to encourage continued engagement and self-management.

Assessments were completed in-app at baseline and at Weeks 2, 4, and 8.

No Intervention: Wait-list Control

Participants in the wait-list control group did not receive the intervention during the initial 8 weeks. Instead, they were asked to complete the same assessments at baseline, Weeks 2, 4, and 8 via survey links delivered by text message. After Week 9, participants were granted access to the *DodaMe* app.

7. Outcome Measures

Primary Outcome:

- Stress: Perceived Stress Scale–10 items (PSS-10, Korean version)

Range: 0–40 (higher = greater stress)

Time Frame: Baseline, Weeks 2, 4, and 8

Secondary Outcomes:

- Depression: Patient Health Questionnaire–9 items (PHQ-9, Korean version)

Range: 0–27 (higher = more severe depression)

Time Frame: Baseline, Weeks 2, 4, and 8

- Anxiety: Generalized Anxiety Disorder–7 items (GAD-7, Korean version)

Range: 0–21 (higher = more severe anxiety)

Time Frame: Baseline, Weeks 2, 4, and 8

- Resilience: Brief Resilience Scale (BRS, Korean version)

Range: 1.0–5.0 (higher = greater resilience)

Time Frame: Baseline, Weeks 2, 4, and 8

8. Sample Size and Randomization

A total of 261 individuals were screened. Of these, 50 were excluded (46 scored below 14 on the PSS-10, 4 declined randomization). The final sample included participants who provided informed consent and were assigned de-identified IDs.

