Participants were randomized to either the intervention group or the wait-list control group using simple randomization (<https://www.randomizer.org/>). Randomization was conducted by a research assistant not involved in data collection or outcome assessment. The principal investigator remained blinded to the allocation process to minimize bias.

An a priori power analysis (G*Power 3.1, repeated-measures ANOVA) indicated a minimum of 128 participants (64 per group) was required to detect a medium effect ($f = 0.25$) with 80% power at $\alpha = 0.05$.

9. Data Collection and Management

Data were collected via the mobile application and online surveys. All data were de-identified at export, and participants were assigned unique IDs. Only the principal investigator and a designated data manager had access to the de-identified dataset.

All study records will be securely stored for three years after study completion in compliance with institutional and national guidelines. After this retention period, electronic files will be permanently deleted, and physical records securely destroyed.

10. Statistical Analysis Plan

All analyses will follow the intention-to-treat (ITT) principle, including all randomized participants with available data. Descriptive statistics will summarize baseline demographic and clinical characteristics.

Primary Analysis

- The primary outcome is perceived stress (PSS-10).
- Changes in stress scores across time points (Baseline, Weeks 2, 4, and 8) between the intervention and wait-list control groups will be examined using generalized estimating equations (GEE) with an appropriate correlation structure to account for repeated measures.

Secondary Analyses

- Depression (PHQ-9), anxiety (GAD-7), and resilience (BRS) will be analyzed in the same manner as the primary outcome.
- Effect sizes and 95% confidence intervals will be reported for all outcomes.

Handling of Missing Data

- Missing data will be addressed using multiple imputation methods, assuming data are missing at random (MAR). Sensitivity analyses will be conducted to assess the robustness of findings.

11. Adverse Events / Safety Monitoring

Although classified as minimal risk, safety procedures were implemented. All research staff were licensed mental health professionals. Participants were provided with direct contact information for the research team to report discomfort or adverse experiences.

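### Section 10 claims intention-to-treat but admits only randomized participants with undefined available data, which can remove app non-installers from the intervention arm alone

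*Combined protocol and SAP*

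**What the plan says.** Section 10 (Statistical Analysis Plan) sets the analysis population in one sentence: "All analyses will follow the intention-to-treat (ITT) principle, including all randomized participants with available data". It does not say whether the data in question are the screening score, the baseline assessment or any follow-up. The same section plans multiple imputation under a missing-at-random assumption without naming the set to be imputed. It adds "Sensitivity analyses will be conducted to assess the robustness of findings", with no method given.

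Section 6 (Interventions) describes how data arise in each arm. "Participants assigned to the intervention group received a text message with a link to install the" *DodaMe* program, and for that arm "Assessments were completed in-app at baseline and at Weeks 2, 4, and 8". Wait-list participants were asked to "complete the same assessments at baseline, Weeks 2, 4, and 8 via survey links delivered by text message". No other route is described for an intervention participant who does not install. Section 9 lists the app and online surveys as the data sources and does not say otherwise.

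Section 5 requires a PSS-10 score of at least 14, so everyone eligible has a score before assignment. Section 8 gives 261 screened and 50 excluded, but neither the number randomized nor the split by arm.

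**The concern.** Intention-to-treat protects the comparison because membership of each arm is fixed at assignment. Here the qualifying phrase ties membership to having data. In one arm, having data after assignment requires the participant to take the first step of the treatment, which is installing the app. In the other arm it requires only answering a survey link. An intervention participant who ignores the install link has no trial assessment. An equally unmotivated wait-list participant may still answer one survey and be counted.

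At stake is the meaning of the PSS-10 result. The intervention arm could become those who took up the app, compared with nearly everyone assigned to wait, and the result would still be labelled intention-to-treat. Because numbers by arm are not given, a reader could not see that this had happened.

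**Working it through.** **1. The plan's own figures.** Section 8 gives 46 + 4 = 50 exclusions and 261 − 50 = 211 remaining. The number randomized is not stated; I assume all 211, about 105 intervention and 106 wait-list. The planned minimum of 128 reproduces as a two-sided two-group *t*-test at d = 2 × 0.25 = 0.50: 64 per group, power 0.801. Power is not the problem here. If 20% of 105 drop out of the set, 84 against 106 still gives power 0.926 at d = 0.50. The problem is selection.

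**2. The two arms side by side (Sections 5 and 6).**

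| | Intervention | Wait-list |
|---|---|---|
| Score before assignment | screening PSS-10 | screening PSS-10 |
| Baseline and Weeks 2, 4, 8 | in the app | text-message survey link |
| Step needed first | install after assignment | none |
| Person who does not take that step | no trial assessment | not applicable |

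**3. Overstatement when non-installers gain nothing.** Let *p* be the share of the intervention arm that never installs and *D* the effect in installers. The effect in everyone assigned is (1 − *p*) × *D* + *p* × 0. Dropping non-installers estimates *D*, if installers would otherwise have changed as the wait-list does. The relative overstatement is 1/(1 − *p*) − 1.

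- *p* = 0.10: 1/0.90 − 1 = 11%
- *p* = 0.20: 1/0.80 − 1 = 25%
- *p* = 0.30: 1/0.70 − 1 = 43%

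The values of *p* are assumptions.

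**4. What imputation does to it.** Take *D* = 0.50 SD and *p* = 0.20, with installers and non-installers alike at screening.

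- True effect in everyone assigned: 0.80 × 0.50 + 0.20 × 0 = 0.40
- Non-installers dropped: 0.50
- Non-installers imputed within arm from the screening score: 0.80 × 0.50 + 0.20 × 0.50 = 0.50
- Non-installers imputed from the wait-list arm: 0.80 × 0.50 + 0.20 × 0 = 0.40

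Within-arm imputation gives non-installers the outcomes of installers, so the 25% overstatement stays. Imputing from the wait-list arm removes it.

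**5. No true effect.** Suppose non-installers are worse than installers by *b* SD at baseline and *f* SD at follow-up, and the wait-list is fully observed. Dropping them shifts the intervention mean in the app's favour by *p* × *b* at baseline and *p* × *f* at follow-up. A comparison at follow-up alone is biased by *p* × *f*: with *p* = 0.10 to 0.30 and *f* = 0.3 to 0.5 (assumed), that is 0.03 to 0.15 SD. Section 10 plans to compare changes across time points, baseline included, so the relevant bias is *p* × (*f* − *b*). It is zero if the disadvantage is stable (*f* = *b*) and equals the follow-up figure only if the whole disadvantage lies in change (*b* = 0).

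**The case against.** The strongest reply is that the sentence need not exclude anyone. Every randomized participant should have a screening PSS-10, which is data, and imputation could run over all of them. This stands as a possible reading, so a reader who infers that the plan definitely drops non-installers goes further than the documents do. But the plan does not say that the screening score counts or that imputation covers everyone. If the screening score did count, the qualifying phrase would exclude nobody and serve no purpose.

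A reader might also take Section 8 as a competing definition of the analysis set, since it says "The final sample included participants who provided informed consent and were assigned de-identified IDs". The documents do not support that. The sentence follows the screening exclusions and precedes the account of randomization; it describes enrolment.

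A third tempting inference is an inflated false-positive rate. For a single follow-up comparison, with bias *p* × *f* and standard error √(1/*n*₁ + 1/106) for *n*₁ = 94, 84 or 74, the two-sided 5% test would reject 5.5% to 16.8% of the time; at *p* = 0.20 and *f* = 0.5 it is 10.5%. Those rates do not carry over to the planned change contrast, where a stable difference in level cancels. Loss of similar people from the wait-list arm would shrink the bias further.

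Finally, it can be said that simply keeping non-installers and imputing them under the plan's assumption would not cure the overstatement. Step 4 of the working confirms this, and the fix allows for it.

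**Conclusion.** The point holds as an undefined analysis set whose natural reading works differently in the two arms. The plan permits a comparison that depends on uptake to be reported as intention-to-treat; it does not compel one.

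If non-installers gain no benefit and are otherwise similar to installers, the overstatement is 11%, 25% or 43% at 10%, 20% or 30% non-installation. The true rate is not in the documents, so the actual size is unknown. With no true effect, neither the size nor the direction of bias can be fixed from the documents: it depends on whether non-installers differ in change and not only in level, and it may be near zero. The change is worth making because it is cheap and the label matters, not because a large bias has been shown.

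**What to change.** In Section 10:

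- Define the analysis set as all randomized participants, in the group assigned, whether or not the app was installed or any post-randomization assessment was completed.
- State that multiple imputation covers all of them and that the screening PSS-10 is in the imputation model.
- Make one of the sensitivity analyses already promised impute non-installers' outcomes from the wait-list arm. This fits the case where a person who never installs gains nothing; it does not correct for unmeasured differences in prognosis.
- Label the analysis of participants with available data as supportive, not intention-to-treat.

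Also report the numbers randomized, installed and analysed by arm. The randomized total should be 211 if nobody else was lost between screening and assignment.

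No new data are needed. The cost is a few sentences and a little more imputation work, with a possibly smaller estimate and a slightly wider interval.

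### Section 10 does not name the PSS-10 test that decides the primary question and treats Baseline as a response time point; name one test and use baseline PSS-10 as a covariate

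*Combined protocol and SAP*

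**What the plan says.** **Section 10, Primary Analysis.** PSS-10 is the primary outcome. The comparison is described as "Changes in stress scores across time points (Baseline, Weeks 2, 4, and 8) between the intervention and wait-list control groups will be examined", by GEE with a suitable correlation structure. Baseline appears in the list of time points being compared. No model term, contrast, visit or significance rule is given, and time is not said to be categorical or linear.

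**Section 7.** The PSS-10 entry reads "Time Frame: Baseline, Weeks 2, 4, and 8" and marks no visit as primary.

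**Section 8.** The power statement "indicated a minimum of 128 participants (64 per group) was required to detect a medium effect" (f = 0.25, 80% power, alpha 0.05). It cites a repeated-measures ANOVA but not which effect of that ANOVA was powered.

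**Section 2.** Under Primary Objective, the second bullet is "To assess whether the program improves depression, anxiety, and resilience". Only usability and perceived quality stand under Secondary Objectives. Section 7 lists the same three measures as secondary outcomes. Section 10, under Secondary Analyses, says "Depression (PHQ-9), anxiety (GAD-7), and resilience (BRS) will be analyzed in the same manner as the primary outcome".

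**Tense.** Recruitment and data collection are described in the past tense, the analysis in the future tense.

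**The concern.** Several tests fit the Section 10 sentence: a 3-df group-by-time test with categorical time, a 1-df slope with linear time, or a difference in change at one visit. Each holds 5% if chosen in advance. Choosing after seeing results does not, and no rule covers claims from single visits. Section 10 also promises that "Effect sizes and 95% confidence intervals will be reported for all outcomes", which will probably put visit-level results in front of readers without saying which one counts.

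The choice also affects power. With Baseline as one of the response time points and group means left free there, the group comparison rests on change scores. These use the baseline measurement less efficiently than covariate adjustment does.

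The Section 2 bullet is a smaller matter. It disagrees with Sections 7 and 10 about which outcomes are primary, and a report could cite it in support of a primary claim on another scale.

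**Working it through.** **1. The plan's own figure.** For two groups, f = 0.25 means d = 2 × 0.25 = 0.5. With 64 per group, the two-sided 5% t test has 126 df and noncentrality 0.5 × √(64/2) = 2.83, so power is 80.1%. Thus 128 reproduces as a two-group comparison of one quantity at one time point, with d in SDs of that quantity. As a four-measurement repeated-measures ANOVA with an assumed correlation of 0.5, the same f would need 82 (between-group effect) or 24 (interaction). Section 8 therefore does not identify the intended test.

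**2. False-positive rate if any of three visits may count.** Each test is at two-sided 5% with no true effect. Section 8 does not state sidedness; two-sided is assumed.

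- Independent tests: 1 − 0.95³ = 14.3%.
- Equal correlation r between the visit tests: 1 − ∫ φ(u) [Φ((1.96 − √r·u)/√(1−r)) − Φ((−1.96 − √r·u)/√(1−r))]³ du. This gives 13.6% (r = 0.3), 12.5% (0.5), 10.9% (0.7) and 9.8% (0.8).
- Change-from-baseline contrasts with exchangeable PSS-10 correlation ρ: each change has variance 2(1−ρ), and two changes have covariance 1−ρ. Their correlation is 0.5 whatever ρ is, so the rate is 12.5%.
- The same contrasts under AR(1) by visit order, ρ = 0.3-0.8: about 12% down to 11%.

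**3. Power with and without the baseline covariate.** Effects are in PSS-10 score SDs. The baseline-to-follow-up correlation r, exchangeable across visits, is not in the documents; 0.3-0.7 is assumed. Data are complete.

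At Week 8, the residual variance is 2(1−r) for raw change and 1−r² with the covariate. The ratio is (1+r)/2, that is 0.65, 0.75 and 0.85 at r = 0.3, 0.5 and 0.7.

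For the joint 3-df test, λ = n/[2(1−r)] × [Σμ² − c(Σμ)²/(1+3c)]. Here n is the number per group, c = 1 for changes and c = r with the covariate. With assumed effects 0.125, 0.25 and 0.5, Σμ² = 0.328 and (Σμ)² = 0.766. At r = 0.5 and n = 64, λ = 64 × (0.328 − 0.191) = 8.75 for changes and 64 × (0.328 − 0.153) = 11.2 with the covariate. Power comes from the noncentral chi-square with 3 df.

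| 64 per group | r = 0.3 | r = 0.5 | r = 0.7 |
|---|---|---|---|
| Week 8, raw change, d = 0.5 | 66% | 80% | 95% |
| Week 8, baseline covariate | 84% | 90% | 98% |
| Joint, changes | 54% | 70% | 91% |
| Joint, baseline covariate | 74% | 81% | 94% |

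**4. Larger sample.** Section 8 gives 261 screened and 50 excluded, leaving 261 − 50 = 211, or about 105 per group if all were randomized. The same formulas then give 86-99.6% (change) and 97-99.9% (covariate) at Week 8, and 77-99% and 93-99.6% for the joint test.

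**5. Joint test or single visit.** If the effect peaks at Week 4 and fades (0.25, 0.5, 0.25), then at 64 per group and r = 0.5 the Week 8 change test has about 29% power and the joint change test about 65%. A single visit does better only if it is the right one.

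**The case against.** The strongest reply is that Section 10 does describe one comparison. It names an outcome, two groups, four time points and a model, and the obvious analysis is a group-by-time test, which holds 5%. That stands: the inflation arises only if the analysts later do something that the plan does not describe. But the test is not named, categorical and linear time give different tests, and a significant 3-df result does not by itself show that stress fell. Visit contrasts will be needed to interpret it, and the plan has no rule for them.

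A reader might infer that the plan lets any significant visit count as success. It does not say so; it only fails to exclude it. The 14.3% end of the range needs uncorrelated tests on the same participants, so about 11-12.5% is the fairer figure for change contrasts.

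A reader might infer from Section 2 that there are four primary outcomes. Sections 7 and 10 agree that PSS-10 is the only one, and no passage makes success depend on any one, or all, of four scales. Error or power figures for such rules would describe no rule in the plan.

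A reader might infer that the trial is underpowered. Section 8 calls 128 a minimum, and 211 people remained after exclusions, so the 64-per-group figures may be pessimistic. The number randomized is not stated.

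Finally, a model that keeps Baseline as a response but constrains the group means to be equal there would gain about as much as the covariate. Section 10 specifies no such constraint.

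**Conclusion.** The point holds in limited form and should be fixed. No passage names the deciding PSS-10 test. The natural reading is sound at 5%, but the wording leaves open a route with a false-positive rate of about 11-12.5%.

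The power gain from the covariate is largest when r is low: at Week 8, 18 percentage points at r = 0.3 and about 2 at r = 0.7. For the joint test it is 20 and 3 points. These gains rest on the assumed correlations, exchangeability, effect pattern and complete data. With 20% missing at Week 8 (assumed, about 51 per group), Week 8 power would be 56-90% for change and 75-94% with the covariate.

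The Section 2 discrepancy is a wording inconsistency, not a second primary family. Nothing in the documents shows that outcomes had been seen by arm; the tense of the text only makes the date of the choice worth recording.

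**What to change.** **Section 10.**

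- Model PSS-10 at Weeks 2, 4 and 8 by GEE, with group, categorical visit, group-by-visit and baseline PSS-10 as a covariate.
- Name one primary test at two-sided 5%. First option, closest to the present text: the joint 3-df test that the group differences at all three visits are zero. Group and group-by-visit terms must be tested together, because the interaction alone would miss a constant effect. State that direction is read from the visit estimates. Acceptable alternative: the group difference at one pre-named visit, such as Week 8, the end of the program.
- Label the remaining visit contrasts as supportive.

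**Section 2.** Move the depression, anxiety and resilience bullet to Secondary Objectives, to match Sections 7 and 10.

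**Record.** Date the change and state whether outcome data had been seen by arm. If they had, report the choice of test as post hoc.

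**Cost.** Wording and a dated note; no change in sample size and no new data. Participants without a baseline score need the multiple imputation that Section 10 already plans. Section 6 has Baseline completed in the app in one arm and by survey link in the other, so confirm that the covariate score precedes program use. The downside is that single-visit results can no longer be claimed as meeting the primary objective, unless that visit is the one named.

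### Section 10 states no baseline adjustment in the GEE; if fitted as an unconstrained group-by-time model, confidence intervals are wider than the collected baseline scores allow (precision only, cheap to improve)

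*Combined protocol and SAP*

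**What the plan says.** Section 10 (Primary Analysis) states: "Changes in stress scores across time points (Baseline, Weeks 2, 4, and 8) between the intervention and wait-list control groups will be examined", and it will do so "using generalized estimating equations (GEE) with an appropriate correlation structure to account for repeated measures". No model terms, baseline covariate, common-baseline constraint or named working correlation are given. Elsewhere in Section 10, baseline data appear only in descriptive summaries.

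The other three scales follow the same plan: "Depression (PHQ-9), anxiety (GAD-7), and resilience (BRS) will be analyzed in the same manner as the primary outcome". Section 10 also promises: "Effect sizes and 95% confidence intervals will be reported for all outcomes". Missing data are to be multiply imputed under MAR.

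Three other places bear on the point:

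- Section 5 excludes on the primary scale ("Score < 14 on the PSS-10"), and Section 8 reports that among 261 screened "46 scored below 14 on the PSS-10, 4 declined randomization". Randomization was simple, so it was not stratified on baseline.
- Section 6 says that participants assigned to the intervention were sent an installation link and completed their assessments, baseline included, inside the app. Controls completed theirs through texted survey links.
- Section 10 is in the future tense, but Section 2 is in the past: "Using a randomized controlled trial design, the study examined the" programme's effectiveness. The documents therefore do not settle whether outcome data have already been examined.

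**The concern.** When Baseline is one of the GEE outcomes and the group means at baseline are left free, the group-by-time term for a visit is, with complete data, the between-group difference in mean raw change. That contrast subtracts the whole baseline score, whereas the best linear adjustment subtracts only the part that predicts follow-up. Unless the two coincide, raw change carries avoidable noise. With complete data, no choice of working correlation recovers it, because the unconstrained model returns the same contrast under each.

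What is at stake is precision. The promised 95% intervals would be wider, and effects smaller than the planned d = 0.5 harder to detect, than the baseline scores already collected would allow. This applies to all four scales.

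**Working it through.** **Plan's own figure.** For two groups and one measurement, f = 0.25 and N = 128 give noncentrality 0.25² × 128 = 8. The noncentral F power at alpha 0.05 is 0.801, so 128 reproduces. For two equal groups, f = 0.25 corresponds to d = 0.5. Section 8 labels the calculation repeated-measures ANOVA, which does not affect this point.

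**Inputs.** Number available: 261 - 50 = 211 (derived). Share removed by the cut-off: 46/261 = 17.6%. SDs and correlations are not in the documents and are assumed throughout. Results are per visit.

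**Formulas.** Let s0 and s1 be the baseline and follow-up SDs and rho their correlation. Per-arm variances are:

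- change contrast: s0² + s1² - 2·rho·s0·s1
- baseline-adjusted contrast: s1²(1 - rho²)
- difference: (s0 - rho·s1)², which is never negative and is zero only if s0 = rho·s1 (for example s0 = 0.8·s1 with rho = 0.8).

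**Scenario A, equal SDs (s0 = s1 = 1).** This is more plausible for PHQ-9, GAD-7 and BRS, which have no entry cut-off, and for PSS-10 if its baseline was re-measured after screening. The variances are 2(1 - rho) and 1 - rho², so the CI ratio is √(2/(1 + rho)).

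| rho | change | adjusted | CI ratio | adjusted N with the same precision as 211 |
|---|---|---|---|---|
| 0.3 | 1.40 | 0.91 | 1.240 | 137 |
| 0.5 | 1.00 | 0.75 | 1.155 | 158 |
| 0.7 | 0.60 | 0.51 | 1.085 | 179 |
| 0.8 | 0.40 | 0.36 | 1.054 | 190 |

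The last column is 211 × adjusted/change.

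**Scenario B, PSS-10 with the screening score as the analysed baseline.** Assume normal scores and equal SDs before selection. Truncating the lower 17.6% leaves a baseline variance ratio v = 0.609. With pre-selection correlation rho, the CI ratio is √(1 + v(1 - rho)/(1 + rho)).

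| pre-selection rho | in-trial rho | CI ratio | adjusted N with the same precision as 211 |
|---|---|---|---|
| 0.3 | 0.24 | 1.152 | 159 |
| 0.5 | 0.41 | 1.097 | 175 |
| 0.7 | 0.61 | 1.052 | 191 |
| 0.8 | 0.72 | 1.033 | 198 |

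Using 46/257, which leaves out the four who declined, changes these ratios by 0.001 or less.

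**Power for d = 0.5.** Noncentral t with noncentrality 0.5/√(V(1/n1 + 1/n2)), where V is the per-arm variance in units of s1²; near-equal arms.

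- 211 analysed, equal SDs, rho 0.3: change 0.5/√(1.40 × 0.01896) = 3.07, power 86.3%; adjusted 0.5/√(0.91 × 0.01896) = 3.81, power 96.6%. At rho 0.5 the figures are 95.1% and 98.7%.
- 211 analysed, Scenario B, rho 0.3: 89.8% against 96.1%.
- 20% dropout (assumed; 0.8 × 211 gives 169), equal SDs, rho 0.3: change 0.5/√(1.40 × 0.02367) = 2.75, power 78%; adjusted 0.5/√(0.91 × 0.02367) = 3.41, power 92%.

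**Mode of assessment.** Suppose app completion shifts scores by a constant m at every visit, relative to the survey link. The change contrast gives (tau + m) - m = tau. Adjusting for the same shifted baseline gives tau + (1 - slope)·m. With equal SDs the slope equals rho, so m = 0.2 SD (assumed) leaves 0.14, 0.10 and 0.06 SD at rho 0.3, 0.5 and 0.7.

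**The case against.** Three objections carry weight.

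**The baseline may not precede allocation.** An in-app baseline cannot come before the installation link, and Section 6 describes that link as sent to people already assigned. The more natural reading is a separate baseline, taken after assignment and in a different mode in each arm. This stands, with two consequences. The 3-15% range for PSS-10, which needs the screening score to be the analysed baseline, is the secondary scenario. And adjustment is not costless: a constant mode effect cancels in the change contrast but not fully in the adjusted one. The documents do not show that a mode effect exists, so it is a downside to guard against and does not defeat the point.

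**The plan never says the model is unconstrained.** Correct. A reader might infer that Section 10 commits the trial to an inefficient model. It does not: it gives no terms, and an adjusted or baseline-constrained GEE is compatible with its wording. The loss is conditional on the usual reading.

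**The trial has enough people anyway.** Largely correct for d = 0.5 without dropout. A reader might infer that the trial is underpowered or the estimate biased. Under randomization the change contrast is valid, and the only computed power below 80% needs low correlation, equal SDs and an assumed 20% dropout together. What remains is interval width and sensitivity to smaller effects.

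**Conclusion.** The point holds as a cheap improvement in precision, conditional on an unconstrained group-by-time model with complete data. Under equal SDs, intervals are about 5-24% wider than a baseline-adjusted analysis would give for rho from 0.8 down to 0.3. For PSS-10 the range is about 3-15% if the screening score is the analysed baseline. Every one of these figures rests on assumed SDs and correlations, and the loss can be zero.

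Power for the planned effect is about 86% or more with 211 analysed, no dropout and rho of at least 0.3. In the least favourable case computed (equal SDs, rho 0.3, 20% dropout) it is about 78% unadjusted against 92% adjusted.

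The documents support neither a claim of bias in the planned analysis nor a claim that the improvement is free of any trade-off.

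**What to change.** If outcome data have not been examined, issue a dated amendment to Section 10. The GEE takes Weeks 2, 4 and 8 as outcomes, with group, visit, group-by-visit, the outcome's own baseline and baseline-by-visit as terms. Apply it to PSS-10, PHQ-9, GAD-7 and BRS, put matching terms in the imputation model, and report adjusted group differences with 95% intervals. In a check on one simulated complete data set of 211, this form gave identical estimates and standard errors under independence, exchangeable and AR(1) working correlations.

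A common-baseline-mean model is a safe alternative only with a named exchangeable or unstructured working correlation. Under independence it reduces to the raw follow-up difference, whose interval at rho 0.7 with equal SDs is √(1/0.60) = 1.29 times that of the change contrast.

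State which score is the baseline, and when and how it was collected in each arm. For PSS-10, use the pre-randomization screening score as the covariate if it is available, because allocation cannot have affected it. That choice does not remove a mode difference at follow-up: a constant shift m would then stay in the adjusted contrast in full. So report the change-score contrast as a sensitivity analysis on every scale.

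If outcome data have been examined, keep the planned model as primary and report the adjusted model as a labelled sensitivity analysis.

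The cost is an amendment, a changed model formula and matching imputation terms, or otherwise one extra labelled analysis per scale. No new data are needed. Which visit or combination of visits is the primary contrast is a separate choice for the sponsor.
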